2 DEFINITION OF ANALYSIS SETS

2.1 Analysis plan

Data analysis will be performed separately for each module or study part and an abbreviated CSR will be written.

2.2 Analysis sets

All patients who receive any amount of study treatment will be included in the safety analysis. For the safety summaries, patients who received study treatment will be presented by module, by part, by cohort and planned starting dose level and dose frequency. Actual dose level and frequency received by patients within each planned cohort will be summarised separately.

For all efficacy analyses, and for baseline and demography summaries, patients are classified according to the module, part, cohorts and the dose they were randomised/assigned to (i.e. the planned treatment/dose level/dose schedule)

The plasma concentrations of AZD7648 and PLD for each scheduled time point will be summarised by module, cohort (dose regimen) and Cycle/PK day (single dose or multiple dose) based on the pharmacokinetics set. The dosing regimen used throughout the PK outputs includes both the dose level and dose frequency of the analyte and should be the planned (protocol scheduled) dosing regimen, although ad hoc summary tables and figures may be requested to include data from patients from a different cohort who were either mis-dosed or where the dose level was the same but the frequency was different (would apply to single dose PK data only).

Details of the analysis sets are presented in [Table 2](#).

Table 2: Analysis sets

Analysis Set	Definition
Enrolled	All patients who signed the informed consent.
Safety set	All patients who received at least 1 dose of any study treatment
Pharmacokinetics (PK) set	All patients who received at least 1 dose of any study treatment with at least one reportable post first dose

	concentration without any protocol deviations that might affect PK.
Evaluable for objective response set	All patients who had a measurable baseline disease ^[a] by RECIST 1.1 assessment and received at least one dose of any study treatment.
Evaluable for efficacy set	All patients who received at least 1 dose of any study treatment and have a baseline tumour assessment according to RECIST 1.1.
DLT evaluable set ^[b]	All patients who received at least 1 dose of any study treatment and either experienced DLT during the cycle 0 or 1, or who completed minimum safety evaluation requirements and has received at least 75% of the total amount of planned dose of AZD 7648 (and PLD for combination Module 1). In the event of an intra-patient dose escalation, such patients will not be evaluable for DLT at the escalated dose.
Pharmacodynamics set	All patients who received at least 1 dose of of any study treatment with at least one reportable pharmacodynamic measurement

^[a] Measurable disease is defined as having at least one measurable target lesion, not previously irradiated, which is ≥ 10 mm in the longest diameter (LD) (except lymph nodes which must have short axis ≥ 15 mm).

^[b] This will be derived directly from the most recent safety review committee meeting minutes prior to data cut off.

Upon database release for each module, protocol deviations and analysis set outputs will be produced and will be sent to AZ for review. Prior to database lock, an analysis set classification meeting will be arranged to discuss the outputs and decide which patients and/or patient data will be excluded from certain analyses. Decisions made regarding the exclusion of patients and/or patient data from analyses will be made prior to database hard lock and will be documented and approved by AZ.

A summary on which analysis set will be used for each outcome variable is provided in [Table 3](#).

Table 3: Summary of outcome variables and analysis sets

Outcome variable	Analysis Sets
Disposition	Enrolled
Demography and baseline characteristics	Safety
Safety data	
Exposure	Safety
Adverse Events	Safety
Prior/Concomitant Medication	Safety
Laboratory measurements	Safety
Vital Signs/ECG/Physical examination	Safety
Echocardiogram	Safety
ECOG PS	Safety
DLTs	DLT evaluable set
4 β -hydroxy cholesterol ratio in plasma	Pharmacokinetics set
Efficacy Data	
Best Objective Response	Evaluable for objective response set Evaluable for efficacy set
Objective Response Rate	Evaluable for objective response Evaluable for efficacy set
Change in tumour size	Evaluable for objective response
Duration of Response	Evaluable for objective response Evaluable for efficacy
PFS	Safety /Evaluable for efficacy
Overall survival	Safety
Pharmacokinetics	
Pharmacokinetic concentrations and parameters	Pharmacokinetics set
Pharmacodynamics	
PDc analysis will be presented in a separate document.	PDc related population will be defined in a separate document dedicated to PDc.
Exploratory biomarkers	

Outcome variable	Analysis Sets
CCI [REDACTED]	CCI [REDACTED]
CCI [REDACTED]	

2.3 Protocol deviations

A list of all protocol deviations will be reviewed and decisions regarding how to handle these deviations will be documented by the study team physician, clinical pharmacology scientist and statistician prior to database lock.

The following general categories (not an exhaustive list) may be considered as important protocol deviations (IPDs) and will be programmatically derived by data management from the electronic case report form (eCRF) and impact harmony data, unless otherwise stated. These will be summarised and listed in the CSR as appropriate. All study specific IPDs will be summarised and listed as per latest corporate reporting standards. Global pandemic (Covid-19) related IPDs will be listed only.

- Patients who deviate from key entry criteria per the CSP.
- Patients who received a different dose than their assigned one or miss a dose.
- Patients missing important protocol required safety assessments (vital signs, clinical chemistry / haematology parameters, urinalysis, ECGs, sample collection for PK etc.) and having potential important impact on patient safety. Baseline RECIST scan missing or > 28+ days before treatment assignment.
- Baseline RECIST scan missing for > 28 + days before treatment assignment.
- No baseline RECIST 1.1 assessment on or before the date of treatment assignment or no baseline bone scan assessment on or before date of treatment assignment.
- Received prohibited anti-cancer therapy during study treatment period.
- Changes to the procedures that impact the quality of the data or any circumstances that can alter the evaluation of the PK (e.g., sampling processing errors that lead to inaccurate bioanalytical results and incomplete PK profile collects).
- Met study treatment discontinuation criteria but continued study treatment and potentially had major impact to patients' safety according to clinical judgement.

The above list of protocol deviations is not exhaustive and additional important deviations may be added prior to database lock as required. A complete list of important protocol deviations can be seen in PD specification document. The categorisation of the above as important deviations is not automatic and will depend on duration and the perceived effect on safety, efficacy, or evaluability of PK profile. If a patient has a deviation that is considered to critically impact upon PK, affected PK data of that patient will be excluded from summaries and statistical analysis (unless otherwise specified), but will still be reported in the listings. Except for certain deviations affecting PK, deviations will not generally lead to exclusion from the analysis sets. However, the impact on the primary endpoint will be assessed, and if considered necessary sensitivity analysis may be considered. All the important protocol deviations will be summarised for the safety analysis set. During the study, decisions on how to handle errors in treatment dispensing (regarding continuation/discontinuation of study treatment or, if applicable, analytically) will be made on an individual basis with written instruction from the study team leader and/or statistician.

In addition to the programmatic determination of the deviations above, other study deviations captured from the CRF module for inclusion/exclusion criteria will also be summarised and listed for protocol deviation reviews. All other deviations that are not important protocol deviations will be termed ‘Other Study Deviations’. Any other deviations from monitoring notes or reports will be reported in an appendix to the CSR.

3 DESCRIPTION OF VARIABLES

3.1 General principles

Data cut off

Data analysis will be performed separately for each module, study part or cohort, and a CSR may be written for each module separately. One administrative analysis is planned see Section 5.

Baseline measurements and change from baseline variables

Baseline (for both safety and efficacy assessments) will be the last non missing value obtained prior to the first dose administration of study medication on cycle 0 day 1. Any information taken after first dose of study medication on cycle 0 day 1 will be regarded as post baseline information. If two visits are equally eligible to assess patient status at baseline (e.g. screening and baseline assessments both on the same date prior to first dose/administration with no washout or other intervention in the screening period), the average should be taken as the baseline value. For non-numeric laboratory tests (i.e., some of the urinalysis parameters) where taking an average is not possible then the best value would be taken

as baseline as this is the most conservative. In the scenario where there are two assessments on cycle 0 day 1, one with time recorded and the other without time recorded, the one with time recorded would be selected as baseline. If no value exists before the first dose/administration, then the baseline value will be treated as missing.

In all summaries change from baseline variables will be calculated as the post baseline value minus the value at baseline.

Percentage (%) change from baseline = $[(\text{post baseline value} - \text{baseline value}) / \text{baseline value}] \times 100$.

Study day

The study day describes the day of the event or assessment date, relative to the reference start date. The study day is calculated as:

- The date of the event (i.e. visit date, onset date of an event, assessment date etc.) – reference start date + 1 if the event is on or after the reference start date;
- The date of the event (i.e. visit date, onset date of an event, assessment date etc.) – reference start date if event precedes the reference start date.

The reference date for all assessments except for tumour assessments, will be the start of the study treatment in cycle 0 (i.e., cycle 0, day 1). There is no study day 0 for this study. Date of cycle 1, day 1 dosing will be considered as the start date for the calculation of efficacy endpoints (tumour response, PFS), which follows CSP visit window starting from cycle 1, day 1. The study day will be displayed in the data listings. If an event starts before the reference start date, the study day displayed on the listing will be negative.

Time Windows

Time windows will need defining for any presentations that summarise values by visit.

Given the washout period between Cycle 0 and Cycle 1 can vary between patients (3-7 days per CSP) and therefore study day of Cycle 1 Day 1 onwards will vary, for the purposes of windowing assessments the study day of visits from Cycle 1 Day 1 onwards will be adjusted in order to allow the same window to be applied across patients. This will not impact on study day displayed in listings and will be used only by programming as an intermediate step to assign analysis visits. The amount to adjust the study day by will be derived assuming the planned day for Cycle 1 Day 1 is day 8 for all patients:

Adjustment (days) = 8 – actual Cycle 1 Day 1 study day

Study day for all safety assessments from Cycle 1 Day 1 onwards will be adjusted by this amount when assigning assessments to analysis visits. Actual, unadjusted study day will be presented in listings.

The following conventions should apply:

- Inclusion within the time window should be based on the actual date and not the intended date of the visit.
- The visit window following baseline will be constructed as per [Table 4](#) for the safety assessments
- For summaries showing the maximum or minimum values, the maximum/minimum value recorded on treatment will be used (regardless of where it falls in an interval).
- Listings should display all values contributing to a time point for a patient.
- Often the most meaningful summaries focus on extreme values rather than summaries at each visit but if summaries over time are felt to be required:
- For visit based summaries
 - If there is more than one value per patient within a time window then the closest value to the scheduled visit date should be summarised, or the earlier, in the event the values are equidistant from the nominal visit date. The listings should highlight the value for the patient that contributed to the summary table, wherever feasible. Note: in summaries of extreme values, all post baseline values collected are used including those collected at unscheduled visits regardless of whether or not the value is closest to the scheduled visit date
- For summaries at a patient level, all values should be included, regardless of whether they appear in a corresponding visit-based summary, when deriving a patient level statistic such as a maximum.

Table 4: Visit windowing (safety analysis)

Cycle	Target Day	Analysis visit	Analysis Visit Window
	screening	Baseline	Day -28 to Cycle 0 Day 1 (pre-dose)
C0	Day 1 (pre-dose)		No analysis visit window: First day of intake of AZD7648

C0	Day 2	Cycle 0 Day 2	C0D1 + 1 day
C0	Day 3	Cycle 0 Day 3	C0D1 + 2 days
C0	Day 4	Cycle 0 Day 4	C0D1 + 3 days
C1	Day 1	Cycle 1 Day 1	No analysis visit window: Monotherapy: First day of restart of AZD7648 after C0 Combinations: Day 1 of associated anticancer agent or first day of restart of AZD7648 after C0 whichever comes first
C1	Day Y	Cycle 1 Day Y	If Y=3 then Day 2 to Day 4 If Y=7 then Day 2 to Day 7
C1	Day 8	Cycle 1 Day 8	^a Last day of previous interval + 1 day to Day 11
C1	Day 15	Cycle 1 Day 15	Day 12 to Day 18
C1	Day 22	Cycle 1 Day 22	Day 19 to C2D1 – 2 days if following cycle Otherwise Day 19 to C1D1+26 days (last cycle)
C2	Day 1	Cycle 2 Day 1	From: Monotherapy: C1D1 + 28 – 1 day or (first day of intake of AZD7648 after C1D1+28) - 1 day; if AZD7648 is off on C1D1+28-1 day. Combinations: (Day 1 of associated anticancer agent for C2 or C1D1 + 28) – 1 day; if associated anticancer agent stopped;

			
or
 
(first day of intake of associated anticancer agent after C1D1+28) – 1 day; if associated anticancer agent is off since C1D1+28-1 day
 
To:
 
Monotherapy: C1D1 + 28 + 1 day
 
or
 
(first day of intake of AZD7648 after C1D1+28) +1 day if AZD7648 is off on C1D1+28-1 day
 
Combinations: (Day 1 of associated anticancer agent for C2 or C1D1 + 28) +1 day; if associated anticancer agent stopped.
 
or
 
(first day of intake of associated anticancer agent C1D1+28) +1 day; if associated anticancer agent and off on C1D1+28-1 day.

C2	Day 15	Cycle 1 Day 15	C2D1 + 11 day to C2D1 + 17 days
Cx (≥3)	Day 1	Day1 of any cycle ≥ 3	
From:
 
Monotherapy: Cx-1D1 + 28 – 2 days
 
or
 
first day of intake of AZD7648 after Cx-1D1+28) – 2 days; if AZD7648 is off on Cx-1D1+28-1 day.
 
Combinations: (Day 1 of associated anticancer agent for Cx or Cx-1D1 + 28) -2 days; if associated anticancer agent stopped
 
or

			
(first day of intake of associated anticancer agent after Cx-1D1+28) – 2 days; if associated anticancer agent is off on Cx-1D1+28-1.
 
To:
 
Monotherapy: Cx-1D1 + 28 + 2 days
 
or
 
first day of intake of AZD7648 +1 day after C1D1+28; if AZD7648 is off on C1D1+28-1 day.
 
Combinations: (Day 1 of associated anticancer agent for Cx or Cx-1D1 + 28) +2 days; if associated anticancer agent stopped.
 
or
 
(first day of intake of associated anticancer agent after Cx-1D1+28) +2 days; associated anticancer agent is off on Cx-1D1+28-1 day.

-	-	IP Disc ^[b]	IP Disc + 1 day
		28 day safety follow-up after IP Disc	
IP Disc +28 -7 days
 
To
 
ID Disc + 28 +7 days

^[a] Previous interval is C1D1.

^[b] Investigational product discontinuation.

Visit windowing for radiological tumour evaluations

The radiological tumour assessments done within 28 days prior and up to pre-dose on cycle 0 day 1 will be considered as baseline. In case of multiple evaluations in the above time period, the value closest to cycle 0, day 1 will be taken as baseline.

A windowing rule will be applied and will follow the protocol allowed visit window; therefore, any RECIST scan performed within ± 1 week of the protocol scheduled visit will be used for that visit. Given

scans will be done relative to Cycle 1 Day 1, the adjustments described for safety assessments will be done when windowing target lesion data.

Handling Missing data

No missing data will be imputed with the exception of the imputation rules described below.

Imputation for partial dates of adverse events, concomitant medication and death

Start and stop dates are collected on the CRF and measures will be taken to minimize missing in data collection. In case of partial information in these dates, the following rules will be used to impute the dates.

If start date is partial:

- Missing day - impute the 1st of the month unless month is same as month of first dose of study drug then impute first dose date.
- Missing day and month – impute 1st January unless year is the same as first dose date then impute first dose date.
- Completely missing – impute with date of first dose of the study treatment, unless the end date suggests it could have started prior to this in which case impute with 1st January of the same year as the end date.
- Imputed start date should be no later than the end date.

For missing diagnostic dates, if day and/or month are missing use 01 and/or Jan. If year is missing, put the complete date to missing. Imputed dates will be used in the calculation of time since diagnosis.

If stop date is partial:

- Missing day - Impute the last day of the month unless both the month and the year are the same as the last dose date or the planned analyses data cut-off date, then impute the last dose date or the planned analyses data cut-off date.
- Missing day and month – impute 31st December unless the year is the same as the last dose date or the primary analysis data cut-off date then impute the last dose date or the primary analysis data cut-off date.
- Completely Missing – need to look at whether the AE/medication is still ongoing before imputing a date and also when it started in relation to study drug. If the ongoing flag is missing then assume that AE is still present / medication is still being taken (i.e. do not impute a date).

Flags will be retained in the database indicating where any programmatic imputation has been applied, and in such cases, any durations would not be calculated unless otherwise specified.

- If a patient is known to have died where only a partial death date is available then the date of death will be imputed as the latest of the last date known to be alive +1 from the database when the date is completely missing. Otherwise, the death date using the available information provided:
 - a. For Missing day only – using the 1st of the month
 - b. For Missing day and Month – using the 1st of January

Imputation for Laboratory Values Outside of Quantification Range

Missing safety data will generally not be imputed. However, safety assessment values of the form of “< x” (i.e., below the lower limit of quantification) or > x (i.e. above the upper limit of quantification) will be imputed as “x” in the calculation of summary statistics but displayed as “< x” or “> x” in the listings. Values of “<=x” or “>=x” will be imputed as well. Note that 0 should not be used as an imputed value in case the endpoint requires a log transformation.

Time unit

A year length is defined as 365.25 days. A month length is 30.4375 days (365.25/12). If duration is reported in months, duration in days will be divided by 30.4375. If duration is reported in years, duration in days will be divided by 365.25.

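### SAP Table 4's Cycle 1 visit windows do not fit the day scale on which the SAP applies them, so scheduled safety results land under the wrong visit

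*SAP*

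**What the plan says.** SAP section 3.1 counts study day from the first dose in Cycle 0. Because the washout before Cycle 1 varies, it defines an adjustment of 8 minus the patient's actual C1D1 study day, "assuming the planned day for Cycle 1 Day 1 is day 8 for all patients". It then says: "Study day for all safety assessments from Cycle 1 Day 1 onwards will be adjusted by this amount when assigning assessments to analysis visits". Listings keep the unadjusted day.

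Table 4 gives the windows. Its Cycle 1 limits are mostly bare days:

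- Day Y: days 2 to 4 if Y=3, or 2 to 7 if Y=7.
- Day 8: "Last day of previous interval + 1 day to Day 11", with footnote a adding "Previous interval is C1D1".
- Day 15: "Day 12 to Day 18".
- Day 22: from day 19 to two days before C2D1, or to C1D1+26 if Cycle 1 is the last cycle.

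The remaining rows are tied to C0D1, C1D1, C2D1 or the previous cycle's Day 1. If several values fall in one window, "the closest value to the scheduled visit date should be summarised".

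For Day 1 of Cycle 3 onwards in monotherapy with AZD7648 interrupted, the lower limit is built on "first day of intake of AZD7648 after Cx-1D1+28", minus 2 days. The upper limit is built on "first day of intake of AZD7648 +1 day after C1D1+28". The row for Cycle 2, target Day 15, has limits C2D1+11 to C2D1+17, but its analysis visit is named Cycle 1 Day 15.

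**The concern.** The adjustment puts C1D1 at day 8 for every patient, yet the bare-day limits surround target days 8, 15 and 22 as counted from C1D1 = day 1. No sentence says the limits are cycle days or that 7 is subtracted before they are applied. A programmer following the text shifts Cycle 1 results by about one row.

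Safety is the primary objective, and the SAP commits to by-visit summaries of vital signs, laboratory values, creatinine clearance, ECG and ECOG performance status. The Core Module schedule (protocol Table 1) plans Cycle 1 ECG and ECOG after Day 1 only at Visit Y and Day 8, so the Day 8 results would be shown at Day 15, where none is planned. In Combination Module 1 Part A (protocol Table 13) they are planned only at Visit Y, and would be shown at Day 8 or Day 15.

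The anchor fault in the Cycle 3 onwards row can separately lose a delayed Day 1 visit, and the mislabelled Cycle 2 row reuses the name of a genuine Cycle 1 visit.

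**Working it through.** **Inputs** (all SAP 3.1 and Table 4): adjusted day = study day + (8 − actual C1D1 study day); the Cycle 1 limits above; 28-day cycles.

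**1. The scale on which the table works.** With C1D1 = 1 and no Visit Y, the windows are Day 8 = 2–11, Day 15 = 12–18 and Day 22 = 19–27; C2D1 follows at 28–30. Targets 8, 15 and 22 each fall in their own row, and Day 15 is exactly ±3. Trying every C1D1 position from −5 to 11, only 0 and 1 put all targets (including Y=3 and Y=7) in their own rows, and only 1 centres Day 15.

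**2. The scale the text prescribes.** Cycle day k becomes adjusted day k + 7 whatever the washout. For example, with C1D1 on study day 4 the adjustment is +4 and C1D8 is 11 + 4 = 15; with C1D1 on study day 9 it is −1 and C1D8 is 16 − 1 = 15. With C1D1 = 8 and C2D1 = 36, the Day 8 row starts at 9 (footnote a) and the Day 22 row ends at 36 − 2 = 34.

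| Actual visit | Adjusted day | Row it falls in |
|---|---|---|
| Y=3 | 10 | Day 8 (9–11) |
| Y=7 | 14 | Day 15 (12–18) |
| C1D8 | 15 | Day 15 (12–18) |
| C1D15 | 22 | Day 22 (19–34) |
| C1D22 | 29 | Day 22 (19–34) |

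Subtracting 7, the rows hold these actual cycle days: Day 8 = 2–4, Day 15 = 5–11, Day 22 = 12–27. The Day Y row (2–4 or 2–7) ends before C1D1 at day 8 and holds nothing. Taking the scheduled date of Day 22 as the protocol date, the closest-value rule keeps C1D22 and drops C1D15; if the C1D22 value is missing, C1D15 is shown as Day 22.

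**3. Cycle 3 onwards, monotherapy, drug interrupted.** Take C1D1 = 8, C2D1 = 36, Cycle 3 due on 36 + 28 = 64, patient off drug on day 63, restart on day 64 + d. The lower limit is 64 + d − 2 = 62 + d. The interrupted-drug upper limit applies only if the patient was off drug on 8 + 28 − 1 = 35. If on drug that day, the default upper limit is 36 + 28 + 2 = 66.

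| d | Restart day | Window | Result |
|---|---|---|---|
| 1 | 65 | 63–66 | captured |
| 2 | 66 | 64–66 | captured |
| 3 | 67 | 65–66 | visit outside |
| 4 | 68 | 66–66 | visit outside |
| 5 | 69 | 67 to 66 | inverted |

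If the patient was off drug on day 35 and restarted at C2D1, the upper limit is 37 or 38, depending on whether *after* includes day 36, so the d = 5 window runs from 67 to 37 or 38. An intermittent monotherapy cohort could meet the off-drug condition with no delay at all, giving 62–63 to 37–38. Protocol 6.1.2 permits such cohorts, but SAP 3.2.1.1 describes the core module as continuous.

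**4. Overlap.** On the C1D1 = 1 scale, footnote a starts the Day 8 window on day 2, so it shares days 2–4 (Y=3) or 2–7 (Y=7) with Day Y, and the Visit Y value qualifies for both rows.

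**The case against.** The best defence is that Table 4's columns are cycle and target day, so a sensible programmer would read the bare days as cycle days, and the Cycle 1 rows would then work apart from the overlap. An always-empty Day Y row would also be noticed. That reading is plausible, and the table specifications are in a separate document not available here, so actual mislabelling cannot be asserted; it follows only if the rule is applied as written. But the reading contradicts the stated rule. It also leaves the adjustment nothing to do in Table 4, because rows tied to cycle dates are unaffected by any shift. Nothing ensures that two programmers would depart from the text in the same way.

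It is also fair that the scale fault and the overlap cannot occur together: read literally, the Day Y and Day 8 windows do not meet (2–7 against 9–11). The overlap appears once the scale is corrected, and only where Visit Y is used, so the two need fixing together. The overlap is small: where a Day 8 value exists, the closest-value rule selects it.

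The Cycle 3 onwards slip looks like text carried over from the Cycle 2 row; every other limit in its row uses the previous cycle's Day 1 and 2 days. That makes the intent clear but leaves the printed limit wrong.

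Finally, the SAP applies the same adjustment to target lesion windows, so changing the constant everywhere would reach beyond safety. Confining the change to the Cycle 1 safety rows avoids this.

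**Conclusion.** The concern holds. On the SAP's stated scale, Visit Y, Day 8 and Day 15 of Cycle 1 all miss their own rows; only Day 22 keeps its correct label. One upper limit, one label and one overlap also need correction. The consequences rest on the text being programmed as written and, for the Cycle 3 example, on the illustrative dates used.

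The reach is limited to descriptive by-visit safety summaries. Adverse event tables, listings, maximum/minimum summaries and DLTs (taken from the Safety Review Committee minutes) do not change, nor do the date-anchored rows apart from the Cycle 3 onwards limit and the Cycle 2 label. No efficacy or dose-escalation conclusion depends on it. It should still be corrected before the tables are run, because these summaries report primary-objective data.

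**What to change.** 1. For safety assessments on or after C1D1, assign the Cycle 1 rows by cycle day (date − C1D1 + 1, that is, an adjustment of 1 − actual C1D1 study day). Keep the Cycle 0 rows on C0D1 dates and leave the target lesion windowing as it is. Alternatively keep day 8 and add 7 to the bare-day limits only: Day Y 9–11 (Y=3) or 9–14 (Y=7), Day 8 ending at 18, Day 15 19–25, Day 22 from 26. The limits C2D1−2 and C1D1+26 stay unchanged. State the scale in Table 4.
2. Amend footnote a so that, when Visit Y is used, the Day 8 window starts the day after the Day Y window: cycle day 5 if Y=3, cycle day 8 if Y=7.
3. In the Cycle 3 onwards monotherapy upper limit for interrupted drug, tie both the anchor and the condition to the previous cycle's Day 1 + 28 and use +2 days. A restart on day 69 then gives 67–71.
4. Rename the analysis visit in the Cycle 2 Day 15 row to Cycle 2 Day 15.

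With changes 1 and 2, cycle days 8, 15 and 22 and Visits Y=3 and Y=7 each fall in their own row. The cost is one programming constant for the Cycle 1 rows and four edits to Table 4, with no new data.
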